4 PARTICIPANT CRITERIA

4.1 Study Population

The study population of particular interest is the group of male participants with symptomatology consistent with Chronic Prostatitis (CP) or Chronic Pelvic Pain Syndrome (CPPS). Each potential study participant must meet the following set of eligibility criteria in order to be entered in the RCT.

4.1.1 Inclusion Criteria

1. Participant has signed and dated the appropriate Informed Consent document.
2. Participant is a male.
3. Participant must have had symptoms of discomfort or pain in the pelvic region for at least a three (3) month period within the last six (6) months.
4. Participant has at least a moderate overall score on the NIH-CPSI (overall score ≥ 15 out of a potential of 0 – 43 points).

4.1.2 Exclusion Criteria

Any participant satisfying any one of the following criteria will **NOT** be eligible to participate in the RCT.

1. Participant has a history of prostate, bladder or urethral cancer.
2. Participant has inflammatory bowel disease (such as Crohn's disease or ulcerative colitis, but not irritable bowel syndrome).
3. Participant has undergone pelvic radiation or systemic chemotherapy.
4. Participant has undergone intravesical chemotherapy.
5. Participant has been treated with intravesical BCG.
6. Participant has been treated for unilateral orchialgia without pelvic symptoms.
7. Participant has an active urethral stricture.
8. Participant has a neurological disease or disorder affecting the bladder.
9. Participant has undergone TURP, TUIP, TUIBN, TUMT, TUNA, balloon dilation of the prostate, open prostatectomy or any other prostate surgery or treatment such as cryotherapy or thermal therapy.
10. Participant has a neurological impairment or psychiatric disorder preventing his understanding of consent and his ability to comply with the protocol.
11. Participant has liver disease.
12. Participant has a known allergy or sensitivity to ciprofloxacin hydrochloride (CIPRO®), tamsulosin hydrochloride (FLOMAX®) or any of their known components.
13. Participant has a history of seizure disorder.
14. Participant is taking theophylline, phenytoin, probenecid or warfarin.
15. Participant requires ongoing use of magnesium, aluminum, or calcium-containing antacids.

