3 STUDY AGENTS

3.1 Ciprofloxacin (CIPRO®)

Despite the fact that most urologists do not perform bacteriologic localization studies(10), the most common therapy for chronic prostatitis is antibiotics(11) and the most common antibiotic in use is ciprofloxacin. The advantages of ciprofloxacin are 1) excellent penetration into the prostate(12), 2) broad spectrum coverage of typical uropathogens as well as chlamydia and 3) high rates of bacterial eradication in participants with chronic bacterial prostatitis(13;14). The most common justification for treating CP participants with antibiotics is the belief that many of these participants have an infection due to cryptic or difficult to culture microorganisms. Indeed, culture of prostatic biopsy tissue in men with negative prostate fluid culture often demonstrates bacteria(15) and bacterial DNA can be isolated from prostate fluid(16) or prostate tissue(17) in a significant proportion of men with culture negative prostatitis. Whether bacteria detected in this manner represent true infection or colonization that is unrelated to symptoms is an issue that has still not been settled.

An alternate explanation for the symptomatic improvement that some CPPS participants achieve with ciprofloxacin could be its direct anti-inflammatory effect. Men with CPPS have documented elevations of inflammatory cytokines such as IL-1, IL-8 and TNF in their prostate fluid(18) and semen(19) as well as elevations in markers of oxidative stress(20). Interestingly, quinolones such as ciprofloxacin have been shown to directly inhibit IL-1 and IL-8 expression from in vitro studies(21;22). Successful treatment with antibiotics also lowers the level of prostatic oxidative stress(20). **(See Appendix D).**

Considering the prevalence of antibiotics as a treatment agent for men with chronic prostatitis and potential mechanisms effect, the objective of this study is to determine a definitive answer to the question of whether this treatment should be considered a guideline for standard therapy for chronic prostatitis.

Studies of quinolones in men with CPPS suggest that if an impact on symptoms is seen, the effect is detected by four (4) weeks ([name], personal communication). Therefore we believe that six (6) weeks of therapy should be sufficient to detect an improvement.

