5.2 Risks of Ciprofloxacin (CIPRO®)

Ciprofloxacin is a synthetic fluoroquinolone antimicrobial agent with a broad spectrum of activity against aerobic bacterial organisms. The principal risks of ciprofloxacin use are as follows:

- Hypersensitivity to ciprofloxacin can occur. This can result in skin rashes or even severe anaphylactic reactions even after a single dose. Such severe reactions are very rare but participants should discontinue the drug if a skin rash or any other evidence of sensitivity to the drug occurs.
- Pseudomembranous colitis can occur after treatment with ciprofloxacin, as with most antimicrobial agents. This can result in severe diarrhea due to overgrowth of *Clostridium difficile* in the colon because of the removal of normal bacterial flora by ciprofloxacin. Participants should contact their physician if persistent diarrhea occurs after taking the drug.

- Ciprofloxacin can cause hypersensitivity to sunlight. Participants should avoid excessive exposure to sunlight or ultraviolet light while taking the drug. The drug should be discontinued if phototoxicity, such as sunburn, occurs.
- Central nervous system effects can occur with ciprofloxacin, including lightheadedness, dizziness, nervousness, anxiety, agitation, insomnia, nightmares or paranoia. Rarely, seizures or convulsions have been reported in participants taking ciprofloxacin. A history of seizure disorder should be reported to the physician prior to instituting therapy with ciprofloxacin.
- Ciprofloxacin may increase the effect of caffeine or the drug theophylline, used for asthma. Caffeine should be used with caution in the participant taking ciprofloxacin and the concomitant use of theophylline and ciprofloxacin may require dosage modification of theophylline.
- Rarely, participants taking ciprofloxacin have developed problems with tendons, including rupture or spontaneous tendon injury. Participants taking ciprofloxacin should discontinue the drug at the first sign of inflammation, pain or rupture of a tendon. If this occurs they should also rest, refrain from exercise and report the event to their physician immediately.

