Bone and Joint Infections caused by *Enterobacter cloacae*, *Serratia marcescens*, or *Pseudomonas aeruginosa*.

Infectious Diarrhea caused by *Escherichia coli* (enterotoxigenic strains), *Campylobacter jejuni*, *Shigella boydii* *, *Shigella dysenteriae*, *Shigella flexneri* or *Shigella sonnei* * when antibacterial therapy is indicated.

Typhoid Fever (Enteric Fever) caused by *Salmonella typhi*.

NOTE: The efficacy of ciprofloxacin in the eradication of the chronic typhoid carrier state has not been demonstrated.

Uncomplicated cervical and urethral gonorrhea due to *Neisseria gonorrhoeae*.

*Although treatment of infections due to this organism in this organ system demonstrated a clinically significant outcome, efficacy was studied in fewer than 10 patients.

If anaerobic organisms are suspected of contributing to the infection, appropriate therapy should be administered.

Appropriate culture and susceptibility tests should be performed before treatment in order to isolate and identify organisms causing infection and to determine their susceptibility to ciprofloxacin. Therapy with CIPRO® may be initiated before results of these tests are known; once results become available appropriate therapy should be continued. As with other drugs, some strains of *Pseudomonas aeruginosa* may develop resistance fairly rapidly during treatment with ciprofloxacin. Culture and susceptibility testing performed periodically during therapy will provide information not only on the therapeutic effect antimicrobial agent but also on the possible emergence of bacterial resistance.

CONTRAINDICATIONS

CIPRO® (ciprofloxacin hydrochloride) is contraindicated in persons with a history of hypersensitivity to ciprofloxacin or any member of the quinolone class of antimicrobial agents.

WARNINGS

THE SAFETY AND EFFECTIVENESS OF CIPROFLOXACIN IN PEDIATRIC PATIENTS AND ADOLESCENTS (LESS THAN 18 YEARS OF AGE), PREGNANT WOMEN, AND LACTATING WOMEN HAVE NOT BEEN ESTABLISHED. (See **PRECAUTIONS: Pediatric Use Pregnancy, and Nursing Mothers** subsections.) The oral administration of ciprofloxacin caused lameness in immature dogs. Histopathological examination of the weight bearing joints of these dogs revealed permanent lesions of the cartilage. Related quinolone- class drugs also produce erosions of cartilage of weight-bearing joints and other signs of arthropathy in immature animals of various species. (See **ANIMAL PHARMACOLOGY**.)

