Convulsions, increased intracranial pressure, and toxic psychosis have been reported in patients receiving quinolones, including ciprofloxacin. Ciprofloxacin may also cause central nervous system (CNS) events including: dizziness, confusion, tremors, hallucinations, depression, and, rarely, suicidal thoughts or acts. These reactions may occur following the first dose. If these reactions occur in patients receiving ciprofloxacin, the drug should be discontinued and appropriate measures instituted. As with all quinolones, ciprofloxacin should be used with caution in patients with known or suspected CNS disorders that may predispose to seizures or lower the seizure threshold (e.g. severe cerebral arteriosclerosis, epilepsy), or in the presence of other risk factors that may predispose to seizures or lower the seizure threshold (e.g. certain drug therapy, renal dysfunction). (See **PRECAUTIONS: General, Information for Patients, Drug Interactions** and **ADVERSE REACTIONS**.)

SERIOUS AND FATAL REACTIONS HAVE BEEN REPORTED IN PATIENTS RECEIVING CONCURRENT ADMINISTRATION OF CIPROFLOXACIN AND THEOPHYLLINE. These reactions have included cardiac arrest, seizure, status epilepticus, and respiratory failure. Although similar serious adverse effects have been reported in patients receiving theophylline alone, the possibility that these reactions may be potentiated by ciprofloxacin cannot be eliminated. If concomitant use cannot be avoided serum levels of theophylline should be monitored and dosage adjustments made as appropriate.

Serious and occasionally fatal hypersensitivity (anaphylactic) reactions, some following the first dose, have been reported in patients receiving quinolone therapy. Some reactions were accompanied by cardiovascular collapse, loss of consciousness, tingling, pharyngeal or facial edema dyspnea, urticaria, and itching. Only a few patients had a history of hypersensitivity reactions. Serious anaphylactic reactions require immediate emergency treatment with epinephrine. Oxygen, intravenous steroids, and airway management, including intubation, should be administered as indicated.

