In this model, mice treated with ciprofloxacin alone did not develop skin or systemic tumors. There are no data from similar models using pigmented mice and/or fully haired mice. The clinical significance of these findings to humans is unknown.

Fertility studies performed in rats at oral doses of ciprofloxacin up to 100 mg/kg (0.8 times the highest recommended human dose of 1200 mg based upon body surface area) revealed no evidence of impairment.

Pregnancy: Teratogenic Effects. Pregnancy Category C: Reproduction studies have been performed in rats and mice using oral doses up to 100 mg/kg (0.6 and 0.3 times the maximum daily human dose based upon body surface area, respectively) and have revealed no evidence of harm to the fetus due to ciprofloxacin. In rabbits, ciprofloxacin (30 and 100 mg/kg orally) produced gastrointestinal disturbances resulting in maternal weight loss and an increased incidence of abortion, but no teratogenicity was observed at either dose. After intravenous administration of doses up to 20 mg/kg, no maternal toxicity was produced in the rabbit, and no embryotoxicity or teratogenicity was observed. There are, however, no adequate and well-controlled studies in pregnant women. Ciprofloxacin should be used during pregnancy only if the potential benefit justifies the potential risk to the fetus (See **WARNINGS**.)

Nursing Mothers: Ciprofloxacin is excreted in human milk. Because of the potential for serious adverse reactions in infants nursing from mothers taking ciprofloxacin, a decision should be made whether to discontinue nursing or to discontinue the drug, taking into account the importance of the drug to the mother.

Pediatric Use: Safety and effectiveness in pediatric patients and adolescents less than 18 years of age have not been established. Ciprofloxacin causes arthropathy in juvenile animals. (See **WARNINGS**.)

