FLOMAX® (tamsulosin HCl) capsules are indicated for the treatment of the signs and symptoms of benign prostatic hyperplasia (BPH). FLOMAX capsules are not indicated for the treatment of hypertension.

CONTRAINDICATIONS

FLOMAX capsules are contraindicated in patients known to be hypersensitive to tamsulosin HCl or any component of FLOMAX capsules.

WARNINGS

The signs and symptoms of orthostasis (postural hypotension, dizziness and vertigo) were detected more frequently in FLOMAX capsule treated patients than in placebo recipients. As with other alpha-adrenergic blocking agents there is a potential risk of syncope (see ADVERSE REACTIONS).

Patients beginning treatment with FLOMAX capsules should be cautioned to avoid situations where injury could result should syncope occur.

PRECAUTIONS

General

- 1) *Carcinoma of the prostate:* Carcinoma of the prostate and BPH cause many of the same symptoms. These two diseases frequently co-exist. Patients should be evaluated prior to the start of FLOMAX capsules therapy to rule out the presence carcinoma of the prostate.

- 2) *Drug-Drug Interactions*: The pharmacokinetic and pharmacodynamic interactions between FLOMAX capsules and other alpha-adrenergic blocking agents have not been determined. However, interactions may be expected and FLOMAX capsules should NOT be used in combination with other alpha- blocking agents.

The pharmacokinetic interaction between cimetidine and FLOMAX capsules was investigated. The results indicate significant changes in tamsulosin HCl clearance (26% decrease) and AUC (44% increase). Therefore, FLOMAX capsules should be used with caution in combination with cimetidine, particularly at doses higher than 0.4 mg.

Results from limited *in vitro* and *in vivo* drug-drug interaction studies between tamsulosin HCl and warfarin are inconclusive. Therefore, caution should be exercised with concomitant administration of warfarin and FLOMAX capsules.

(See also drug-drug interaction studies in CLINICAL PHARMACOLOGY Pharmacokinetics subsection.)

Information for Patients (see Patient Package Insert)

Patients should be told about the possible occurrence of symptoms related to hypotension such as dizziness when taking FLOMAX capsules, and they should be cautioned about driving, operating machinery or performing hazardous tasks.

Patients should be advised not to crush, chew or open the FLOMAX capsules.

Laboratory Tests

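### Exclusion 12 leaves out the quinolone-class contraindication in the protocol's own Appendix D, so a man with a past reaction to another quinolone can be randomised to ciprofloxacin

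*Protocol*

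**What the plan says.** **Allergy exclusion.** Section 4.1.2, item 12, bars a man if "Participant has a known allergy or sensitivity to ciprofloxacin hydrochloride (CIPRO®), tamsulosin hydrochloride (FLOMAX®) or any of their known components". It names two drugs and their components, and no drug class.

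**Ciprofloxacin label.** The Contraindications section of Appendix D states that the drug is "contraindicated in persons with a history of hypersensitivity to ciprofloxacin or any member of the quinolone class of antimicrobial agents". Its Warnings add: "Serious and occasionally fatal hypersensitivity (anaphylactic) reactions, some following the first dose, have been reported in patients receiving quinolone therapy".

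**Risk text in the body.** Section 5.2 says of hypersensitivity to ciprofloxacin: "This can result in skin rashes or even severe anaphylactic reactions even after a single dose". It tells participants to stop the drug at a rash or other evidence of sensitivity.

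**Tamsulosin label.** Appendix E states: "FLOMAX capsules are contraindicated in patients known to be hypersensitive to tamsulosin HCl or any component of FLOMAX capsules". Item 12 reproduces this in full.

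**Background treatment.** Section 3.1 notes that "the most common therapy for chronic prostatitis is antibiotics(11) and the most common antibiotic in use is ciprofloxacin".

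**Age.** The demographic requirement in 4.1.1 is "Participant is a male", with no lower age limit among the listed criteria. Appendix D says: "Safety and effectiveness in pediatric patients and adolescents less than 18 years of age have not been established". Appendix E says tamsulosin is not indicated in pediatric populations.

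**The concern.** The written eligibility criteria decide who may be randomised. If they are narrower than the labelled contraindication of a study drug, the protocol permits dosing that its own appendix rules out. Here the missing part is a past reaction to a quinolone other than ciprofloxacin.

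The harm can be serious and can come with the first dose. A rule to stop at the first sign acts only after exposure. Treatment is also masked, and unmasking under Section 8.5 needs the medical monitor's approval, so site staff would not at first know whether a reacting participant had received ciprofloxacin.

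Earlier quinolone exposure is plausible in this population. Section 3.1 describes antibiotics as the usual therapy and refers to studies of quinolones in men with this condition. The deferral criteria look back only four weeks.

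**Working it through.** This is mainly a comparison of texts. The plan gives no figure to reproduce.

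**1. Scope of item 12 against Appendix D.**

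| Past reaction to | Item 12 excludes? | Label contraindicates? |
|---|---|---|
| Ciprofloxacin | Yes | Yes (Appendix D) |
| Another quinolone | No | Yes (Appendix D) |
| Tamsulosin or a capsule component | Yes | Yes (Appendix E) |

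Only the second row disagrees.

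**2. Does the reference to components cover the class?** No. Section 5.3 and Appendix E both use the word for ingredients of the formulation. Another quinolone is not an ingredient of the ciprofloxacin tablet.

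**3. Does anything else close the gap?**
- *Deferrals 2 and 3 (4.1.3)* concern ciprofloxacin or other antimicrobial use in the past four weeks. They postpone entry after recent use and do not address a past reaction.
- *Section 5.2* describes reactions to ciprofloxacin itself and adds no exclusion.
- *Screening Visit 1 (7.2)* takes a general and genitourinary history, with emphasis on diseases and surgery. Drug allergy is not named.
- *Screening Visit 2 (7.3)* confirms the same criteria.
- *Section 7.4* has a man randomised once he meets all the criteria. The exclusions contain no general clause for investigator judgement.

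**4. Deliberate choice or oversight?** Items 13 to 15 carry over several warnings and precautions from Appendix D: seizure history, theophylline, phenytoin, probenecid, warfarin and antacids. The class contraindication ranks above these in the label, yet only half of it was carried over and no reason is given. That looks like an oversight.

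**5. Size.** Inputs: 184 men, four equal arms (46 each), ciprofloxacin in two of them (Sections 7.4, 10 and 10.2).
- Places with ciprofloxacin: 184 × 2/4 = 92.
- Chance that one affected man is assigned ciprofloxacin: 92/184 = 50%.
- If *k* affected men were enrolled, the chance that at least one is assigned ciprofloxacin is 1 − 0.5^*k*, treating assignments as independent:
  - *k* = 1: 1 − 0.5 = 50%
  - *k* = 2: 1 − 0.25 = 75%
  - *k* = 3: 1 − 0.125 = 87.5%

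The values of *k* are assumed, because the document gives no prevalence. Allocation is by permuted blocks within centre (Section 10.1), so independence is an approximation. Men falling in the same block would have a somewhat higher chance that at least one is assigned ciprofloxacin.

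**The case against.** The mismatch in wording is not in dispute. The case on the other side concerns its weight.

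- **Allergy history catches few reactions.** The same paragraph of the Appendix D Warnings says that few of the patients with serious reactions had a history of hypersensitivity. Screening on history would therefore prevent only a minority, and the stopping rule in 5.2 has to cover the rest. This stands as a limit on the benefit. It does not remove the contraindication.
- **The residual group is small.** Section 3.1 says ciprofloxacin is the antibiotic most used, so most past quinolone reactions among candidates may be to ciprofloxacin itself, which item 12 already excludes. This also stands, and the number left over is unknown.
- **Unseen material may help.** The consent form, the screening form and the Manual of Procedures are not visible and might ask about quinolone allergy. Investigators also hold Appendix D as part of the protocol. An alert clinician may well stop such a man, but would have no written criterion to cite.
- **The table over *k* is only illustrative.** Agreed. The informative figure is the 50% for each affected man.
- **The age point is minor.** Agreed. It rests on a warning, not a contraindication, and the consent pages may set a limit. It carries no weight in the conclusion.
- **No effect on the analysis.** True, but an eligibility rule that allows contraindicated dosing does not need an effect on power to require correction.

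**Conclusion.** The concern holds, and the criterion must be corrected. Item 12 is narrower than the contraindication in the protocol's own Appendix D, and no visible text makes up the difference. An otherwise eligible man who reacted to another quinolone, with no antimicrobial use in the past four weeks, passes the written criteria and then has a 50% chance of being assigned ciprofloxacin.

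The conclusion rests on reading components as ingredients, which is how the protocol uses the word elsewhere, and on the visible text only. How many men are affected cannot be computed from the document. The severity comes from the nature of the possible harm and the explicit contraindication, not from an expected count.

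**What to change.** In Section 4.1.2, item 12, insert *or any other quinolone* after ciprofloxacin and leave the rest unchanged. Carry the same words into the eligibility checklist so that they are confirmed before randomisation. As a separate tidy-up, add a minimum age of 18 years to Section 4.1.1 and to the checklist.

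The cost is one reworded exclusion, one added inclusion line and a checklist update, with no new test, visit or change to the analysis. A few otherwise eligible men may be lost; the document does not allow that number to be estimated.

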4.1.3 Deferral Criteria

For some conditions, participants may be reconsidered for entry into the trial once the condition has resolved as indicated below.

1. Participant has been treated with tamsulosin hydrochloride (FLOMAX®), doxazosin mesylate (Cardura®), terazosin HCL (Hytrin®), or alpha-blockers in the past four (4) weeks.
2. Participant has been treated with ciprofloxacin hydrochloride (CIPRO®) in the past four (4) weeks.
3. Participant has been treated with antimicrobial agents (oral or parenteral) in the past four (4) weeks.
4. Participant has started, stopped, or changed dose level of **ANY** prostatitis-specific medications within the past four (4) weeks.
5. Participant has had a urinary tract infection, with a urine culture value of >100,000 CFU/ml, within the past three (3) months.

6. Participant has had clinical evidence of urethritis, e.g. including urethral discharge or positive culture, within the past three (3) months, diagnostic of the following sexually transmitted diseases (STDs): gonorrhea, chlamydia, mycoplasma or trichomonas, but not including HIV/AIDS.
7. Participant has had a prostate biopsy in the past three (3) months.
8. Participant has experienced symptoms of acute or chronic epididymitis within the past three (3) months.
9. Participant has begun finasteride (Proscar®) or other androgen hormone inhibitors in the past six (6) months, or stopped finasteride (Proscar®) or other androgen hormone inhibitors within the past six (6) months.
10. Participant has used bioflavonoid agents [Example: Quercetin] in the past two (2) weeks.
11. Participant has been diagnosed with or treated for symptomatic genital herpes in the past twelve (12) months.
12. Participant has been taking zinc or iron supplements within the past two (2) weeks.
13. Participant has been treated with cimetidine in the past two (2) weeks.

